6.5 Sample Size

A sample size of at least 30 has been chosen based on the number or participants required for the purposes of a feasibility assessment.⁹ It is also a practically feasible number of participants to recruit based on annual admission numbers of patients to the RHH and the timeframe of the recruitment period.

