6.7 Outcome Measures

Primary Outcome Measures – success criteria:

- Monitor tolerability for tVNS
 - Symptom severity scores of mild or moderate in less than 1/3 of participants able to report symptoms (based on Likert Scale 1-5; 1 representing no issues; 5 representing severe symptoms)
- Assess study feasibility
 - recruit >1 patient per month of recruitment
 - >80% of recruited patients completing primary outcome measures at 4 weeks follow up

These outcome measures will be collected during the participants inpatient stay over the intervention period using a data collection proforma (appendix) and taken from recruitment records kept contemporaneously. Safety assessment of SAEs / AEs will be collected each intervention day by our research team.

Secondary Outcome Measures:

- Monitor safety criteria for tVNS
 - No SAEs reported to tVNS
 - Unexpected AEs in less than 1/3 of participants
- Explore clinical outcomes including:
 - rates of clinical or radiological DCI (%)
 - inpatient mortality (%)
 - inpatient length of stay (days)
 - rate of complications: seizures, hyponatraemia, rebleed, hydrocephalus (%)
- Outcome measures using questionnaires on discharge and at 1-month
 - Disability assessment: modified Rankin Score, Barthel Index
 - Assess frequency and severity of headache: Likert scale
- Explore mechanisms of action:
 - Inflammatory markers at baseline and 5 days
- o Explore response to tVNS:
 - Near-infrared cerebral spectroscopy
 - Heart rate variability
 - Pupillary reactivity

These will be measured during the inpatient hospital stay up until discharge (Figure 1).

- Outcome measures using questionnaires at on discharge and at 4 week follow-up
 - Disability assessment: modified Rankin Score, Barthel Index
 - Assess frequency and severity of headache: Likert scale (1-10 where 1 is non-existent and 10 is extremely severe)
- Explore mechanisms of action measured at baseline and at the end of intervention (5 days):
 - Inflammatory marker analysis at baseline and 5 days (IL-1B, IL-6, IL-10, TNFa)
 - Concurrent WCC, CRP and infection will be recorded at these time points as these may confound results
- o Explore response to tVNS:
 - Near-infrared cerebral spectroscopy

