6.10 Study Protocol

Patients (or their representatives if they lack capacity) who are eligible for entry into the will be approached by the treating clinical teams with information about the study. Those who are interested will be given an information sheet and time to consider the study. Those keen to participate will sign a consent form (or assent form for those that lack capacity) and baseline outcome measures will be performed.

Enrolled participants will be issued with a study number and randomised 2:1 (SealedEnvelope Ltd) stratified according to age (<65 and ≥ 65 years). They will then receive either active tVNS stimulation (tragus) or sham (earlobe), twice daily for 45 minutes per session for 5 days. We do not anticipate discharges from hospital earlier than 5 days as this is not routine practice in the neurosurgical unit.

Primary outcome measures of tolerability and feasibility will be collected daily by researchers delivering the intervention, and secondary outcome measures will be collected at the end of intervention or on hospital discharge as detailed in figure 2.

Following discharge from hospital participants will return for follow up clinic assessment at 4 weeks where questionnaire measures of functional recovery and adverse event reporting will be undertaken. After this the participants involvement in the study will be complete.

Figure 2: Study Schedule for Outcome Measures

	Baseline visit	Visit 1	Visit 2	Visit 3	Visit 4	Visit 5 (EOT)	discharge	At 4 weeks
Eligibility screening	Х							
Informed consent	Х							
Randomisation	Х							
Socio- demographic data	X							
Clinical data collection	X						X	
Questionnaires: Disability - mRS, BI, headache likert scale	X						X	X
Reporting of side effects, adverse events and tolerability		X	X	X	X		X	X
Intervention reporting – settings delivered, duration of intervention		X	X	X	X			
Pupillometry + recording of prescribed eye drops	X					X		
Heart rate variability	X					X		
fNIRS	Х					X		
Monitor blood test results (secondary outcome measures), collection of data on WCC/CRP and infection status	Х	X	X	X	X		X	
Inflammatory marker analysis	X					Х		

EOT = End of treatment; BI = Barthel Index;

fNIRS = Functional near infra-red spectroscopy

7. Data Management

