7.1 Statistical Analysis

The analyses will be undertaken on statistical software (PRISM) and will compare the two groups. Rates of complications and outcomes will be reported descriptively. Data integrity will be checked by two researchers and inputted contemporaneously. Each researcher will be trained in outcome measures prior to study initiation.

We anticipate approximately 50% of participants will be unable to complete questionnaires due to confusion / low GCS etc. This is exploratory and if this is the case then these outcome measures will not be taken forward in the next stages of future trials. Otherwise we anticipate very few missing data in terms of the primary outcome measures and the objectively measured secondary outcomes due to the fact that we will have a researchers based on the neurosurgical units throughout the recruitment and intervention periods collecting and recording data.

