7.2 Statistical Opinion

This is a pilot study which hopes to form the basis of further grant funding for a larger study. This is a provisional study to demonstrate tolerability and feasibility. Further statistical advice would be sought should further funding be granted for future study. Primary outcome data will be reported descriptively (proportions, %).

Continuous data will be compared using parametric or non-parametric analyses depending on whether data distribution is normal or not. Categorical data will be compared using Chi-square or one-way ANOVA. However, due to the small sample size, appropriate power to detect significant differences for these measures will not be reached. This is primarily an exploratory study and most data will be reported descriptively.

Between group differences in baseline characteristics will be compared using parametric (T-Tests) and non-parametric (Mann – Whitney U, Chi squared) tests, depending on normality of distribution.

A secondary outcome of this study is safety of TVNS in patients who have suffered a subarachnoid haemorrhage. Utilising the definition of SAE, if no SAE's are reported which are deemed related to tVNS by the research team, then we can be 95% confident that the true SAE rate lies between 0 and 12%.¹⁵

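### Figure 2 schedules no WCC, CRP or infection record at Visit 5, when the day-5 inflammatory markers are drawn, although section 6.7 says these are recorded then

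*Protocol*

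**What the plan says.** Protocol section 6.7 lists the marker outcome as "Inflammatory marker analysis at baseline and 5 days (IL-1B, IL-6, IL-10, TNFa"), under the line "Explore mechanisms of action measured at baseline and at the end of intervention (5 days"). Directly below, it adds: "Concurrent WCC, CRP and infection will be recorded at these time points as these may confound results".

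Figure 2 in section 6.10 gives the visit schedule. One row covers the markers. A separate row covers routine bloods and "collection of data on WCC/CRP and infection status".

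On analysis, section 7.1 says: "The analyses will be undertaken on statistical software (PRISM) and will compare the two groups". Section 7.2 says: "Continuous data will be compared using parametric or non-parametric analyses depending on whether data distribution is normal or not". It names no covariate and does not say whether day-5 values or changes from baseline are compared. It also concedes that "due to the small sample size, appropriate power to detect significant differences for these measures will not be reached".

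**The concern.** The protocol itself names WCC, CRP and infection as things that could distort the marker results, and commits to recording them alongside the markers. If the schedule does not call for them at the end-of-treatment draw, a team working from Figure 2 would not collect them there. An analysis plan cannot restore what was never recorded. WCC and CRP might be recovered from hospital results. Infection status at the time of the draw is a judgement best recorded then.

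At stake is the reading of the day-5 markers. A raised IL-6 at end of treatment means something different in a participant with a current infection. The anti-inflammatory rationale for the intervention is explored through these markers.

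A second, smaller matter arises once confounders are named without a stated use. The obvious use, adjusting the day-5 comparison for day-5 CRP, can bias it. The safe and useful covariate, the baseline marker, is collected but not mentioned in section 7.2.

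**Working it through.** The plan gives no SD, target difference, correlation or power figure for the markers, so there is no stated figure to reproduce.

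**Step 1. The two schedule rows side by side (Figure 2).**

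| Row | Baseline | V1 | V2 | V3 | V4 | V5 (EOT) | Discharge | 4 weeks |
|---|---|---|---|---|---|---|---|---|
| Inflammatory markers | X | | | | | X | | |
| WCC/CRP/infection | X | X | X | X | X | | X | |

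Section 6.7 equates 5 days with the end of intervention, and Figure 2 labels Visit 5 as end of treatment, so the day-5 draw is Visit 5. The two rows coincide only at baseline. The nearest records to the day-5 draw are Visit 4, before it, and discharge, which has no fixed date.

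**Step 2. Is the blank specific to this row?** The Visit 5 column is marked for pupillometry, heart rate variability, fNIRS and the markers. The eye-drop record, the other confounder the protocol names, shares the pupillometry row and is therefore scheduled at Visit 5. However, the side-effect row and the intervention-reporting row are also blank at Visit 5, although section 6.7 has adverse events collected on every day of the intervention. The omission may therefore be column-wide.

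**Step 3. What the baseline marker would add.** Let r be the correlation between baseline and day-5 values (on the log scale if logs are used). The documents do not give it; 0.3 to 0.7 is assumed. Compared with day-5 values alone, adjustment multiplies the variance of the treatment difference by 1 − r² and the interval width by √(1 − r²). Compared with change scores, the variance ratio is (1 − r²) / [2(1 − r)] = (1 + r)/2.

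| r | Variance cut vs day-5 only | Width cut vs day-5 only | Variance cut vs change score |
|---|---|---|---|
| 0.3 | 1 − 0.91 = 9% | 1 − 0.954 = 5% | 1 − 0.65 = 35% |
| 0.5 | 1 − 0.75 = 25% | 1 − 0.866 = 13% | 1 − 0.75 = 25% |
| 0.7 | 1 − 0.51 = 49% | 1 − 0.714 = 29% | 1 − 0.85 = 15% |

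These are large-sample ratios. With 30 participants the covariate uses one of 28 residual degrees of freedom, so the gain is a little smaller, most noticeably at r = 0.3.

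In terms of detectable difference (two-sided 5%, 80% power, both assumed), the formula for day-5 values is (1.960 + 0.842) × √(1/n₁ + 1/n₂). Section 6.5 sets the total: "A sample size of at least 30 has been chosen". The synopsis gives 15 per arm and section 6.10 gives 2:1, so both are shown.

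- 15:15: 2.802 × 0.3651 = 1.02 SD. With the baseline covariate: 0.98, 0.89 and 0.73 SD at r = 0.3, 0.5 and 0.7.
- 20:10: 2.802 × 0.3873 = 1.09 SD. With the covariate: 1.04, 0.94 and 0.77 SD.

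**Step 4. Why day-5 CRP should not be a covariate.** Take an assumed model in which treatment lowers the marker by 0.80 and day-5 CRP by 0.50, and a shared factor enters both with weight 0.6. Given arm and baseline, the marker–CRP covariance is 0.6 × 0.6 = 0.36 and the CRP variance is 0.6² + 0.8² = 1.00, so the slope on CRP is 0.36. The CRP-adjusted effect becomes −0.80 − 0.36 × (−0.50) = −0.62. A simulation of this model (20:10, 4,000 runs) gave −0.62 with CRP and −0.80 with the baseline marker alone. If treatment does not affect CRP, both give −0.80.

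**The case against.** The strongest reply is that the text of section 6.7 states the commitment plainly and the figure has merely dropped some marks in one column. That may well be so, and nothing shows a decision not to collect these data. The table was also read from PDF, so the marks should be checked against the original. The contradiction still stands as printed, and staff tend to work from the schedule.

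A reader might go further and infer that the planned analysis discards the baseline marker, or wrongly fails to adjust for the confounders it names. The documents do not support either inference. Section 7.2 is silent on baseline values and does not exclude them. Measuring at baseline and 5 days fits a change-score or adjusted analysis equally well. Covariates are commonly left to a statistical analysis plan, which is not at hand. Section 6.7 promises only that WCC, CRP and infection will be recorded, not that they will be adjusted for, and adjusting for their day-5 values would be inadvisable.

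It is also fair to say that no success criterion depends on the markers, that section 7.2 expects mostly descriptive reporting, and that the precision figures rest on an assumed correlation and do not measure the schedule gap. All of this stands and limits the weight of the point.

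**Conclusion.** The schedule contradiction is confirmed: section 6.7 requires WCC, CRP and infection at the day-5 draw, and Figure 2 does not schedule them at Visit 5. It should be corrected, because data missed at that visit may not be recoverable.

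The baseline covariate is a recommendation, not an error in the plan. Its benefit ranges from slight to substantial across the assumed correlations. The simulated bias from adjusting for day-5 CRP is likewise illustrative: it depends on treatment affecting CRP, which an anti-inflammatory intervention could do.

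Overall impact is low. The markers are an exploratory secondary outcome, and even at r = 0.7 only differences of about 0.73 to 0.77 SD would be detectable with 80% power.

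**What to change.** 1. In Figure 2, mark the WCC/CRP/infection row at Visit 5 (EOT), so that it agrees with section 6.7. Check at the same time whether the side-effect and intervention-reporting rows should also be marked there.
2. State that day-5 infection, WCC and CRP will be described by arm and will not be covariates in the treatment comparison.
3. Recommended: state that each marker will be compared by arm on the log day-5 value, with the log baseline value as covariate, reporting the estimate and 95% interval.

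The cost is one mark in the figure and one or two sentences. The same row is already completed at Visits 1 to 4, and the baseline markers are already measured.

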6.8 Subject Withdrawal, Breaking the Blind and Trial Discontinuation Rules

Participants will be advised that they can withdraw from the study at any time without giving a reason and without this affecting their clinical care. Any data already collected will be analysed with permission from the patient. A member of the research team will confirm the patient is happy to continue with the longitudinal study at their clinical follow up appointments.

We will record data including number of patients admitted with aneurysmal SAH, number eligible, number recruited, dropout rates, and reasons for these. Participants will be given the opportunity to get involved in a public patient involvement group (PPI) at completion of the study.

6.9 Intervention

We are using tVNS settings that are widely used in other neurological conditions (epilepsy, migraine)¹⁴. These include:

- o Pulse width 25ms
- Frequency device default (20 or 25Hz)
- Intensity below pain threshold.
- Frequency 45 minutes twice daily. On the basis of similarity to other studies, practicalities on the ward and clinical scenario

We have chosen a duration of 5 days based on the usual clinical pathway of inpatient management at the Royal Hallamshire Hospital, and have chosen to deliver the treatment twice daily to optimise the dose. This is a pilot study with feasibility outcomes and as such we will be exploring the feasibility of this treatment regimen.

The Parasym Device will be applied to the left tragus (figure 1) as this is the most common site for tVNS delivery in neurological studies and is associated with few afferents to the heart.

The intervention is aimed at supplementing routine clinical care, and as such, the doses of tVNS can be interrupted for care activities (therapy sessions, examinations, assessments etc) and resume afterwards. The overall minute duration will aim to remain 45 minutes twice daily.

[figure not shown]

Figure 1. Anatomy of the ear and the tragus (a). Parasym attached to the tragus (b)

The active intervention will be compared to sham tVNS where the vagal nerve stimulator will be attached to the earlobe instead of the tragus, in keeping with evidence that this does not cause vagus nerve stimulation and is in line with sham methods used in other studies. We do not anticipate that patients will have the intervention long enough to become familiar with the common sensations associated with true tVNS intervention. At the end of the intervention period, participants will be asked if they thought they had received true of sham tVNS to understand the blinding ability of the sham.

We will use the FNIRS Lumo ecosystem (Gower labs) to assess cerebral blood flow in the frontal lobes. We will complete a protocol where 6 optodes are placed bilaterally over the frontal and prefrontal cortices. We will complete and record resting state signals of oxyhaemoglobin and deoxyhaemoglobin for 5 minutes while patients are layed in bed with their eyes closed (or wearing an eye patch). Following the 5-minute rest phase, vagal nerve stimulation or sham stimulation will start

depending on the participants randomisation and signal acquisition will continue for 5 minutes. After this time, the stimulation will cease and a further 5 minutes of resting signal acquisition will be completed. The data acquired during this protocol will undergo processing (adjustment for background and physiological noise) and data analysis using recommended software (Homer 2/3). Data analysis will look to compare signal acquisition between resting and stimulation states and will evaluate any lasting effects of stimulation following termination. We will perform this on the first and last day of the intervention, before and after stimulation respectively.

We will be using Reflex Pupillometry to measure pupillograms in response to a light stimulus during an intervention session for all participants. This will be done at a different time to the Lumo FNIRS assessment. Recording of the pupillary response will follow the following protocol; 3 baseline measures taken 1 minute apart prior to stimulation will represent baseline pupillograms (which will be averaged). Following this, stimulation (active or sham) will start and 3 times pupillograms will be measured at 1 minute intervals following initiation. After completion of the treatment session, 3 further pupillograms separated by 1-minute intervals will be measured - that will constitute the recovery phase. We acknowledge that environmental influences (ambient light intensity, equipment noise and administered medications may confound pupillography, however this analysis is exploratory.

6.10 Study Protocol

Patients (or their representatives if they lack capacity) who are eligible for entry into the will be approached by the treating clinical teams with information about the study. Those who are interested will be given an information sheet and time to consider the study. Those keen to participate will sign a consent form (or assent form for those that lack capacity) and baseline outcome measures will be performed.

Enrolled participants will be issued with a study number and randomised 2:1 (SealedEnvelope Ltd) stratified according to age (<65 and ≥ 65 years). They will then receive either active tVNS stimulation (tragus) or sham (earlobe), twice daily for 45 minutes per session for 5 days. We do not anticipate discharges from hospital earlier than 5 days as this is not routine practice in the neurosurgical unit.

Primary outcome measures of tolerability and feasibility will be collected daily by researchers delivering the intervention, and secondary outcome measures will be collected at the end of intervention or on hospital discharge as detailed in figure 2.

Following discharge from hospital participants will return for follow up clinic assessment at 4 weeks where questionnaire measures of functional recovery and adverse event reporting will be undertaken. After this the participants involvement in the study will be complete.

Figure 2: Study Schedule for Outcome Measures

	Baseline visit	Visit 1	Visit 2	Visit 3	Visit 4	Visit 5 (EOT)	discharge	At 4 weeks
Eligibility screening	Х							
Informed consent	Х							
Randomisation	Х							
Socio- demographic data	X							
Clinical data collection	X						X	
Questionnaires: Disability - mRS, BI, headache likert scale	X						X	X
Reporting of side effects, adverse events and tolerability		X	X	X	X		X	X
Intervention reporting – settings delivered, duration of intervention		X	X	X	X			
Pupillometry + recording of prescribed eye drops	X					X		
Heart rate variability	X					X		
fNIRS	Х					X		
Monitor blood test results (secondary outcome measures), collection of data on WCC/CRP and infection status	Х	X	X	X	X		X	
Inflammatory marker analysis	X					Х		

EOT = End of treatment; BI = Barthel Index;

fNIRS = Functional near infra-red spectroscopy

7. Data Management

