13.	Taking the Work Forward	. 20
14.	Intellectual Property (IP)	. 20
15.	Costing Schedule	. 21
16.	Funding Arrangements	. 21
17.	References	21

1. Study Synopsis/Profile

Study title	Investigating the tolerability and feasibility of transcutaneous vagus nerve stimulation following aneurysmal subarachnoid haemorrhage				
Study short title	tVNS in aSAH				
Study design	Two-arm randomised controlled trial				
Study participants	Inclusion criteria:				
	 Age >18 Admitted to STH neurosurgery Confirmed aneurysmal SAH on vascular imaging Within 5 days of 'Securing' aneurysm (i.e., successfully coiled or surgically following rupture) 				
	Exclusion criteria:				
	 Current or prior use of a vagus nerve stimulation Symptomatic bradycardia or PPM insertion Complete heart block Implantation of any other electrical stimulator (e.g. DBS) 				
Planned sample size	30 participants (15 in each arm)				
Planned study period	36 months				
Planned recruitment period	24 months				
Study assessments	 Deliver TVNS using the parasym device for 45 minutes twice daily for 5 days following aSAH intervention (coiling or clipping) Pulse width 25ms, frequency device standard (25 Hz), at maximum tolerated intensity, or 				

	20MA for patients who cannot report the maximum tolerated intensity • Clinical follow-up on discharge and at 1 month				
Objectives	s Primary				
•	To establish the tolerability, and feasibility of tVNS in patients following aSAH, including;				
	 Monitor tolerability for tVNS Symptom severity scores of mild or moderate in less than 1/3 of participants able to report symptoms Assess study feasibility recruit >1 patient per month of recruitment >80% of recruited patients completing primary outcome measures 				
	Secondary				
	 Monitor safety criteria for tVNS No SAEs reported to tVNS Unexpected AEs in less than 1/3 of participants Explore clinical outcomes including: rates of clinical or radiological DCI inpatient mortality inpatient length of stay Rate of complications: seizures, hyponatraemia, rebleed, hydrocephalus Outcome measures using questionnaires on discharge and at 1-month Disability assessment: modified Rankin Score, Barthel Index Assess frequency and severity of headache: Likert scale Explore mechanisms of action: Inflammatory markers at baseline and 5 days Explore response to tVNS: 				
	 Near-infrared cerebral spectroscopy Heart rate variability Pupillary reactivity 				

2. Research Questions

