Is transcutaneous nerve stimulation a tolerable and feasible intervention to potentially improve clinical outcomes in aneurysmal subarachnoid haemorrhage (aSAH)?

3. Abstract/Summary

Background

Subarachnoid haemorrhage (SAH) is a type of brain bleed, which can be complicated by issues including delayed cerebral ischaemia (DCI) which causes stroke like symptoms, such as weakness, in up to 30% of patients. Current treatments for DCI focus on improving blood supply but fail to address other important factors including reducing inflammation.

Stimulation of a nerve in the neck called the vagus nerve, which can be done through the skin (transcutaneous vagus nerve stimulation, tVNS) is known to relax blood vessels and reduce inflammation and is approved in other conditions such as epilepsy.^{3,4} In animals, vagus nerve stimulation improves survival after aSAH, and is being studied in humans to reduce headaches after aSAH.^{5,6}

There is a theoretical role of tVNS in improving outcome after aSAH. We aim to study whether tVNS is tolerated, and feasible in aSAH.

Methods

This is a single centre, pilot randomised controlled trial (RCT); the participants will receive either tVNS or 'sham' tVNS, twice daily for 45 minutes for 5 days. We will monitor tolerability (symptoms) and feasibility (recruitment rates) for recruited patients. Secondary outcomes will include rates of side effects, complications from SAH, outcomes on discharge and 4 week follow up, and exploration of mechanisms of action and response to tVNS including levels of serum inflammatory markers (IL-1B, IL-4, IL-6, IL-10 and TNFa), functional near infra-red spectroscopy (f-NIRS), heart rate variability (HRV) and pupillary light reactivity (PLR).

Results

Rates of complications, side effects and recruitment will be reported descriptively and we will undertake simple between-group statistical analyses on secondary outcome measures. If proven to be tolerated and feasible, this study will provide the basis for a future larger trial design.

4. Aims of the Study

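### Randomisation is stratified by age group but the planned two-arm tests leave the stratum out, so exploratory comparisons lose precision to the extent that age is prognostic (minor)

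*Protocol*

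**What the plan says.** Section 6.10 states that participants are "randomised 2:1 (SealedEnvelope Ltd) stratified according to age" (<65, ≥65). Age group is the only stratification factor named.

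The analysis text does not mention it again. The Results paragraph of section 3 promises that "we will undertake simple between-group statistical analyses on secondary outcome measures". Section 7.2 says "Continuous data will be compared using parametric or non-parametric analyses depending on whether data distribution is normal or not", and "Categorical data will be compared using Chi-square or one-way ANOVA". The t-test and Mann-Whitney test are named there only for baseline comparisons.

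The protocol also limits what rides on these tests. Section 7.2 reports the primary outcomes as proportions without a test, concedes that the between-arm comparisons will lack power, and calls the study mainly exploratory. Section 7.1 reports complication and outcome rates descriptively. The only confidence statement is the 0 to 12% range for the related-SAE rate if no such event is seen.

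**The concern.** Stratified randomisation makes the arms nearly alike in age mix, so the arm difference varies less between hypothetical repeats of the trial than it would under unrestricted allocation. A plain two-sample test does not know this. It estimates its error from the total spread, including the part due to age group, and so overstates the standard error when age group is prognostic. The p-value is then too large on average, and the precision that stratification could have given goes unused.

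Section 4 wants to explore signals of effect, and section 13 wants the data to support a grant application. With about 30 patients there is little precision to give away. This concerns the randomisation factor, not adjustment for the baseline value of an outcome. It therefore also reaches outcomes without a baseline value, such as length of stay.

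**Working it through.** **Inputs from the protocol.** Two age strata (6.10). Total of at least 30 (6.5). Allocation 2:1 (6.10), although the synopsis gives "30 participants (15 in each arm"); both ratios were run. No standard deviation, effect size, alpha or power is given for any between-arm comparison.

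**Assumptions not in the protocol.** Share aged ≥65: 30% or 50%. Permuted blocks of 6 or 3 (2:1) or 4 (1:1). Share of outcome variance explained by the age stratum, R²: 0 to 0.30. Two-sided 5% level. For power, a 1 SD difference.

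**Step 1: the protocol's one inferential figure.** The exact two-sided upper 95% limit for 0 events in n is 1 − 0.025^(1/n). For n = 30 this is 1 − 0.025^(1/30) = 11.6%, which rounds to the stated 12%. It is a one-sample limit with no arm comparison, so the stratum does not enter it.

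**Step 2: approximation for a continuous outcome.** With arms balanced on age, the true variance of the arm difference is about (1 − R²) times what the unadjusted test assumes. Hence:
- unadjusted / adjusted interval width ≈ 1/√(1 − R²)
- true size of the nominal 5% test ≈ 2 × P(Z > 1.96/√(1 − R²))

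At R² = 0.10: √0.90 = 0.949, so the width ratio is 1/0.949 = 1.054. The threshold becomes 1.96/0.949 = 2.07, giving a size of 3.9%.

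**Step 3: simulation.** N = 30, stratified blocks, pooled t-test against a linear model with arm and stratum; 6,000 trials per setting for size and width, 3,000 for power. Width and size are ranges over all six combinations of ratio, block size and age mix. Power is for blocks of 6 (2:1) or 4 (1:1) with 30% aged ≥65, unadjusted → adjusted.

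| R² | Width ratio, formula | Width ratio, simulated (1 / adjusted-to-unadjusted) | Size, formula | Size, simulated | Power 2:1 | Power 1:1 |
|---|---|---|---|---|---|---|
| 0 | 1.00 | 1.00 | 5.0% | 4.6-5.4% | 70.4 → 70.7% | 75.7 → 75.3% |
| 0.05 | 1.03 | 1.02 | 4.4% | 4.1-4.7% | 70.0 → 71.6% | 75.4 → 76.2% |
| 0.10 | 1.05 | 1.05 | 3.9% | 3.6-4.2% | 71.4 → 75.0% | 76.1 → 79.0% |
| 0.20 | 1.12 | 1.12 | 2.8% | 2.8-3.4% | 72.1 → 79.3% | 76.1 → 83.0% |
| 0.30 | 1.20 | 1.20 | 1.9% | 2.0-2.4% | 72.6 → 84.4% | 77.2 → 87.1% |

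The adjusted model kept a size of 4.5-5.5% throughout. At R² = 0.02 the unadjusted size was 4.5-5.2% and the widths differed by under 1%.

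**Step 4: binary outcomes.** The overall rate was set at 30%, after the upper figure for DCI in section 5, with N = 30, 2:1 and 30% aged ≥65. The size of the unadjusted chi-square was 4.7% with equal rates by age, 4.5% with 25% against 42%, 4.0% with 20% against 53%, and 1.2% with an extreme 10% against 77%. A stratified exact test, run with 40% aged ≥65 and rates of 30/30%, 25/37.5% and 20/45%, had a size of only about 2.4-3.0%. That is further below 5% than the planned chi-square.

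**Step 5: cost of the extra term.** The 95% t multiplier rises from 2.048 (28 df) to 2.052 (27 df), or 0.2%. Section 7.1 expects about half of participants to be unable to complete questionnaires, which leaves about 15. There it rises from 2.160 (13 df) to 2.179 (12 df), or 0.9%. Simulated power at N = 15 and 2:1 went from 38.9% to 38.3% at R² = 0 and from 38.1% to 40.8% at R² = 0.10.

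**The case against.** The strongest reply is that no decision depends on this. The success criteria in section 6.7 contain no between-arm test, the primary outcomes are descriptive, and the protocol already says the comparisons are underpowered. That stands and sets the severity.

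Second, the loss is conditional. Nothing in the documents shows that a two-level age split explains much of the variance in cytokines, heart rate variability, pupillometry or fNIRS, and at 0-2% there is no measurable effect. That stands too. The higher rows of the table are possibilities, not expectations. Even so, the trade is favourable at N = 30, because adjusting costs almost nothing if age turns out not to matter.

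Third, an analysis plan that is not shown may include the stratum, and a parametric analysis does not exclude a model with age in it. This stands in part. But the protocol fixes simple two-group comparisons itself, and chi-square and one-way ANOVA have no place for a stratum. The mismatch is therefore in this document.

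A reader might also infer three stronger points that the documents do not support:
- That the trial's reported intervals will be wrong. No between-arm interval is planned, and the SAE limit is unaffected.
- That DCI, mortality and complications suffer to the same degree. Step 4 shows a small effect unless rates differ strongly by age.
- That every comparison should be stratified. For binary outcomes a stratified exact test would be more conservative than the planned one.

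**Conclusion.** The point holds in a limited form and is minor. The tests named in sections 3 and 7.2 leave out the only randomisation stratum. To the extent that age group is prognostic, standard errors and p-values for the exploratory continuous comparisons are conservative. The error never favours the intervention.

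For N = 30 the excess interval width runs from nil at R² = 0, through about 5% at 0.10, to 20% at 0.30; the true size of a nominal 5% test falls from 5% through about 4% to 2%. These figures rest on assumed R², age mix and block sizes. They are similar at 1:1 and 2:1, so they do not depend on how the separate conflict between the ratio in 6.10 and the arm sizes in the synopsis is resolved.

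It would go too far to say that the p-values will be conservative whatever the outcome, since that needs a prognostic strength the documents do not give. No success criterion changes.

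**What to change.** Add one sentence to section 7.2: any reported between-arm comparison of a continuous outcome uses a linear model with terms for arm and the randomisation age stratum (<65, ≥65), on a transformed scale or replaced by a stratified rank test (van Elteren) if the outcome is skewed. Align the sentence in section 3 with it.

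Leave binary outcomes descriptive, as section 7.1 already has them. An age-stratified estimate may be added as optional, but a stratified exact test should not be required.

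The cost is one degree of freedom, slightly more noticeable for questionnaire outcomes if only about 15 patients complete them. If the named software lacks a stratified rank test, a free package will do. No new data or patients are needed.
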